### **9.5.5 Visit 5 (Day 42 ± 4): Follow-up Phone Call**

A phone call will be conducted approximately 14 days after the subject has completed dosing to follow-up on any new adverse events that may have occurred.

## **9.6 Study Procedures**

### **9.6.1 Informed Consent**

At Visit 1, before performing any study-related procedures the study patient must sign the IRB-approved consent form. If the patient is under the age of majority in the state that the study is being conducted (18 years in most states) then patient's parent or legal guardian must sign the consent form and the patient must sign the assent form. Both the consent and assent forms will be reviewed and approved by an Institutional Review Board before study commencement. No patient will be entered into the study without reading, understanding, and signing an informed consent/assent. For illiterate patients, verbal consent should be obtained in the presence of and be countersigned by a literate witness. If any other language is required, translation will be performed by a certified translator.

### **9.6.2 Demographics**

At Visit 1, each patient shall be required to provide basic demographic information: date of birth, gender, ethnicity and race.

### **9.6.3 Medical History**

At Visit 1 patients will be questioned about personal medical history including psoriasis history and all medication use within the previous 12 weeks.

### **9.6.4 Vital Signs**

The patient's vital signs will be recorded (pulse, blood pressure, temperature and respiration rate) at all clinic visits.

## **CONFIDENTIAL PROTOCOL**

A Randomized, Double-Blind, Placebo-Controlled, Parallel-Design, Multiple-Site Clinical Study to Evaluate the Efficacy and Safety of Desoximetasone Topical Spray, 0.15% (Taro Pharmaceuticals, U.S.A., Inc.) in Patients with Mild to Moderate Plaque Psoriasis

---

### **9.6.5 Height and Weight**

At Visit 1 the subject's body weight (kg) and height (cm) will also be measured while the Subject is lightly clothed (e.g., no coat or shoes). The patient's BSA will be calculated using instructions in Appendix A.

### **9.6.6 Concomitant Medication Use**

At each clinic visit, patients will be questioned about current and concomitant medication use. Patients will also be questioned about ongoing or new concomitant medication use during the treatment period at Visits 2, 3 and 4.

### **9.6.7 Pregnancy Test**

All females of childbearing potential will have a urine pregnancy test performed at Visits 1 and 4. The test must be negative at Visit 1 for the patient to be eligible for inclusion in the study. If the patient is female and not considered of childbearing potential, then the reason must be documented in the patient's source documents.

Any patient who becomes pregnant during the study should be discontinued and end of treatment procedures (Visit 4) completed. The outcome of the pregnancy should be followed by the Investigator to the conclusion of the pregnancy.

### **9.6.8 Dispensing Study Medication**

An Independent Dispenser will dispense study medication at Visit 1, along with dosing instructions. Patients will be instructed to apply the first dose of study medication in the clinic, and the remaining doses at home. The Independent Dispenser will ensure the study medication logs are reported correctly.

### **9.6.9 Collecting Study Drug**

Bottles of study product will be collected at Visit 3 and Visit 4 and checked for compliance or evidence of tampering with the blind.

### **9.6.10 Dosing Instructions and Diary**

Patients will be provided with a dosing diary at Visits 1, 2 and 3 along with instructions on how to complete the diary. Patients will be asked to record the time and date of each dose, AEs, and concomitant medications throughout the study. The diary will be reviewed at each visit by the study staff.

### **9.6.11 Dosing Compliance**

Dosing compliance will be checked by site staff at Visits 2, 3 and 4 by reviewing patient diary entries. Patients will be considered compliant with dosing if they administer 75%-125% of the required number of doses, and did not miss more than 3 consecutive days of dosing.

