### 9.4.1 Treatments Administration

An Independent Dispenser will dispense the study medication and provide instruction on the dosing technique. The patient will be told to spray and gently rub in the study drug (until it is completely absorbed into the skin) to the affected areas twice a day (morning and evening), approximately 12 hours apart, for 28 days. To ensure compliance with the dosing technique, patients will be instructed to apply the medication under the supervision of the Independent Dispenser at the time of enrollment and then twice daily until their next scheduled visit. Patients will be provided with a dosing diary in which they will be required to record dosing dates and times. These diaries should be brought to each visit in order that the study staff may check compliance. At the end of the study, the dosing diaries will be retained in the patient's file as source documentation.

Qualified study patients will be provided with one 100 ml bottle of study medication at Visit 1 along with instructions for dosing. Bottles of study drug should be weighed before dispensing and after they are returned so the weight will be recorded. At Visit 3 (Day 14 ± 2) the first bottle should be collected and new 100 ml bottle of spray should be dispensed along with dosing instructions. This bottle will be returned at Visit 4 (Day 28 ± 2). Based on a maximum of 2 x 3 ml applications/day, 2 x 100 ml bottles of spray should provide sufficient drug for the study. Bottles will be weighed at the time of dispensing and when returned to determine that amount of drug used.

The patient will be informed to avoid smoking and proximity to heat or flame while using the product owing to the flammability of the product.

Treatment compliance will be encouraged by instructing the patient on the proper dosing technique and by the use of the daily diary. Compliance will be assessed by evaluation of the diary and overall exposure to study drug will be assessed by weighing the study drug bottles before and after use (see sections 9.4.5 and 9.6.11).

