#### **10.2 Determination of Sample Size**

The primary analyses of interest are the proportion of patients in the Test and Vehicle treatment groups who are considered to be a Clinical Success and Treatment Success on Day 28.

In-house data from two Phase III studies that evaluated the safety and efficacy of desoximetasone spray 0.25% (twice daily for 28 days) in patients with moderate to severe plaque psoriasis were used for sample size determination. These studies were conducted in support of Taro's NDA #204141, Topicort® (desoximetasone) Topical Spray, 0.25%. In those studies the Clinical Success rates were 31% and 53% for the active product (42% average) and 5% and 18% for the vehicle treatment (12% average), and the Treatment Success rates were 39% and 53% for the active product (46% average) and 7% and 17% for the vehicle treatment (12% average).

Based on the average results from these two studies on the 0.25% spray, the proportion of subjects in the Test group considered a Clinical Success and Treatment Success is expected be 40% or higher and the proportion of subjects in the Vehicle group considered a Clinical Success and Treatment Success is expected to be 12% or less for desoximetasone spray 0.15% in patients with mild to moderate plaque psoriasis. With these assumptions, 50 evaluable subjects in the ITT in each treatment group will demonstrate superiority of the Test to the Vehicle group with 89% power at the 5% level of significance ( $p < 0.05$ , using two-sided Z-test), assuming 100% correlation between Clinical and Treatment Success rates.

To allow for patients who may drop out from the study or are otherwise non-evaluable, up to 120 patients may be enrolled (60 in the Test group and 60 in the Vehicle group).

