### **10.3.2 Per-Protocol (PP) Population**

The PP population is a sub-population of the ITT population and will include:

- Patients who met all inclusion and exclusion criteria and were randomized according to the randomized treatment assignment.
- Patients who applied at least one dose AND had at least one post-baseline evaluation.
- Patients who were compliant with the dosage regimens following randomization.
- Patients who had no major protocol deviations.

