### **Definitions:**

1. Treatment Success: To be considered a Treatment Success the patient's TLSS value at Day  $28 \pm 2$  must be 0 if their baseline TLSS value is 2 and must be 0 or 1 if their baseline TLSS value is  $> 2$  for each of the individual signs and symptoms
2. Treatment Failure: A patient will be considered a Treatment Failure if:
  - a. the patient's TLSS value is  $> 0$  if their baseline TLSS value is 2 or  $> 1$  if their baseline IGA score is  $> 2$  for any of the individual signs and symptoms
  - b. the patient was considered to have an insufficient therapeutic response
3. Clinical Success: To be considered a Clinical Success the patient must have at least a 2-grade improvement from their baseline IGA score. That is, an IGA score of 0 at Day  $28 \pm 2$  if their baseline IGA score is 2 or an IGA score of 0 or 1 at Day  $28 \pm 2$  if their baseline IGA score is 3
4. Clinical Failure: A patient will be considered a Clinical Failure if:
  - a. the patient's IGA score is  $> 0$  if the baseline IGA score is 2 or  $> 1$  if the baseline IGA score is 3
  - b. the patient was considered to have an insufficient therapeutic response

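### The per-protocol compliance rule makes no exception for patients who stop for insufficient response, so PP membership can depend on outcome and the PP sensitivity analysis can be biased

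*Protocol*

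**What the plan says.** Sections 9.1, 9.4 and 9.4.1 set a twice-daily regimen. In 9.4.1 the spray goes "to the affected areas twice a day (morning and evening), approximately 12 hours apart, for 28 days".

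Section 9.6.11 defines compliance, with the gap counted in days: "Patients will be considered compliant with dosing if they administer 75%-125% of the required number of doses, and did not miss more than 3 consecutive". Section 9.4.5 gives the same rule in negative form. Neither section says how many doses are required of a patient who stops early.

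Section 10.3.2 lists among the PP criteria "Patients who were compliant with the dosage regimens following randomization". The bullet before it asks only for at least one dose and at least one post-baseline evaluation. No criterion mentions the reason for stopping.

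Section 10.5 gives two routes to Treatment Failure and two to Clinical Failure. The second route in each case (items 2b and 4b) is that "the patient was considered to have an insufficient therapeutic response".

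Section 10.6 bases the superiority decision on the ITT population with LOCF and names a PP run for sensitivity. It names no other sensitivity analysis. Section 10.3.1 puts every randomized patient in ITT, and 9.3.5 confirms that early stoppers and patients with significant deviations stay there.

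**The concern.** A PP run helps as a sensitivity analysis if patients leave it for reasons unrelated to how they responded. Here the dosing rule can remove a patient because treatment did not work. That patient already has a defined endpoint result, failure on both co-primary endpoints, and does not need to be excluded for want of data.

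The criteria in 10.3.2 also point in two directions. The requirement of a single post-baseline evaluation suggests that some early stoppers belong in PP. The compliance criterion, counted on the full regimen, takes them out. Two analysts could build different PP sets from the same text.

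What is at stake is how the PP result can be read. If failures leave the two arms at different rates, neither agreement nor disagreement with ITT can be interpreted cleanly.

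**Working it through.** **1. The plan's own figure.** Section 10.2 states that "50 evaluable subjects in the ITT in each treatment group will demonstrate superiority of the Test to the Vehicle group with 89% power". The test named there is a two-sided Z-test at the 5% level, and the assumed success rates are 40% on Test and 12% on vehicle. With the pooled variance under both hypotheses, the mean rate is 0.26 and the standard error is √(2 × 0.26 × 0.74 / 50) = 0.0877. Then 0.28 / 0.0877 − 1.96 = 1.23, which gives 89.1% power. The stated 89% is reproduced. It is not in dispute, and 40% and 12% serve below as starting rates.

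**2. What the dosing rule removes, if required doses means the full regimen.**
- Required doses: 2 per day × 28 days = 56.
- Lower limit: 0.75 × 56 = 42 doses, reached after 42 / 2 = 21 days.
- Last dose on Day 7: 14 / 56 = 25%, non-compliant.
- Last dose on Day 14: 28 / 56 = 50%, non-compliant.
- Last dose on Day 24: Days 25 to 28 are missed, which is 4 consecutive days, so the patient fails on the gap rule even with enough doses.
- Last dose on Day 25: 3 days are missed, so the patient passes.

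On this reading, anyone whose last dosing day is Day 24 or earlier is outside PP.

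**3. The other reading.** If required doses means those due up to discontinuation, a patient who stops at Day 14 with no missed dose has 28 / 28 = 100% and can stay in PP. The protocol does not say which count applies.

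**4. Effect on the PP comparison.** Let p be an arm's success rate and f the share of that arm removed as failures. The PP rate is p / (1 − f). The protocol gives no rates of discontinuation for lack of effect, so every f below is an assumption.

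| Removed, Test / Placebo | PP rate, Test | PP rate, Placebo | Difference (points) |
|---|---|---|---|
| 0% / 0% | 40.0% | 12.0% | 28.0 |
| 0% / 10% | 40.0% | 13.3% | 26.7 |
| 5% / 20% | 42.1% | 15.0% | 27.1 |
| 5% / 15% | 42.1% | 14.1% | 28.0 |
| 5% / 10% | 42.1% | 13.3% | 28.8 |
| 10% / 10% | 44.4% | 13.3% | 31.1 |
| 10% / 5% | 44.4% | 12.6% | 31.8 |

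The direction is not fixed because removing failures raises the success rate in whichever arm loses them, by p × f / (1 − f). The starting rate is higher on Test, so a given f moves the Test rate more. At 5% on Test the rise is 0.40 × 0.05 / 0.95 = 2.1 points. At 15% on Placebo it is 0.12 × 0.15 / 0.85 = 2.1 points, and the two cancel.

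**5. No true effect.** With 12% in both arms, removing 5% / 15% gives 12.6% against 14.1%, a difference of −1.5 points. Reversing the removals gives +1.5 points. A spurious PP difference can therefore arise in either direction.

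**The case against.** The strongest reply has four parts.

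- **The denominator.** Compliance is checked visit by visit (9.6.11), Visit 4 records the doses taken since Visit 3 (9.5.4), and early terminators are asked to complete Visit 4 procedures (9.3.5). Counting doses up to discontinuation fits that text, and the patient could then stay in PP. This stands as a possible reading, so the protocol cannot be said to exclude these patients with certainty. The full-regimen count is nevertheless the more natural one, and the choice decides who is in PP.
- **Stopping for lack of effect is not described.** Items 2b and 4b do not say that the patient is discontinued, and the reasons for removal in 9.3.4 name worsening but not insufficient response. That is correct, but the list in 9.3.4 is not exhaustive and patients may withdraw for any reason. Such stops can occur, though their number is unknown.
- **The decision rule is untouched.** Superiority rests on ITT with LOCF. This stands in full.
- **It may belong in the SAP.** Section 10.1 leaves missing, unused and spurious data to the SAP, which is not at hand and may add PP rules or sensitivity analyses. However, the compliance rule and the PP criteria are fixed in the protocol, and it is these that conflict with the endpoint definitions.

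A reader might go further and infer that PP exclusions always shrink the treatment difference. The table shows otherwise: 5% / 15% leaves it at 28.0 points and 10% / 5% raises it to 31.8.

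A reader might also infer that fast responders are systematically lost, because a patient with no lesions left has nowhere to spray and would show a gap in the diary. The text leaves room for this but does not state it. The instruction runs for 28 days, no passage permits stopping on clearance, and affected areas can mean those identified at enrolment. This part is an unresolved ambiguity, and no size of bias can be attached to it.

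**Conclusion.** The point holds in a limited form. Compliance is a condition of PP with no exception for stopping because of insufficient response, and the number of required doses is undefined for early stoppers. On the 56-dose count, a patient who stops at about Day 14 has about 50% and is excluded, although 10.5 defines that patient as a failure on both co-primary endpoints. PP membership can thus depend on outcome, and the PP run can be biased.

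The size and direction are not established. The range of 26.7 to 31.8 points around 28.0 rests on the planning rates and on assumed removal rates, and it shows only that the shift can go either way. It does not follow that the PP analysis is certainly biased or useless. Nothing here affects the ITT conclusion, its power or its type I error. The statement that PP is the only sensitivity analysis applies to this protocol alone.

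The point deserves a change before unblinding, because it concerns the one stated check on the primary result and is nearly free to correct.

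**What to change.** 1. In 10.3.2, state that patients discontinued for insufficient therapeutic response who otherwise meet the PP criteria stay in PP and count as failures.
2. In 9.4.5 and 9.6.11, compute compliance on the doses required up to the day of discontinuation, and apply the gap rule over the same period.
3. As a minor clarification, reconcile the two parts of the application instruction in 9.1 and 9.4.1 (where to apply and for how long) for patients whose lesions clear. How to do so is for the sponsor to decide. Required doses should then be counted in line with that instruction, so that a patient who follows it is not scored non-compliant.

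The cost is a few sentences in 9.1, 9.4.1, 9.4.5, 9.6.11 and 10.3.2. No extra data are needed, provided the date of and reason for stopping are recorded. Section 9.3.5 already requires the reason, and the diary gives dosing dates.

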## **CONFIDENTIAL PROTOCOL**

A Randomized, Double-Blind, Placebo-Controlled, Parallel-Design, Multiple-Site Clinical Study to Evaluate the Efficacy and Safety of Desoximetasone Topical Spray, 0.15% (Taro Pharmaceuticals, U.S.A., Inc.) in Patients with Mild to Moderate Plaque Psoriasis

---

### **9.6.12 Dermatological Assessment**

At Visit 1 a visual inspection to confirm a diagnosis of chronic plaque psoriasis will be performed. At each visit psoriasis will be assessed according to the following measures:

- a) % BSA Assessment: Appendix A
- b) IGA Score: Appendix C
- c) TLSS: Appendix B
- d) PASI Score: Appendix D
- e) Application Site Reactions: Appendix E

Wherever possible, the same Investigator should attempt to perform all IGA exams at all visits for an individual patient.

During the overall dermatological assessment at Visit 1, the Investigator will determine which lesion in his opinion (considering a combination of size and severity of lesional signs and symptoms) is the most severe. This lesion must have an area of at least 5 cm^2 and have a plaque elevation score of at least 2 (mild).

This lesion will be designated the Target Lesion. If possible, the Target Lesion should exclude the elbows and knees. The location of the Target Lesion will be identified using an anatomical chart in the source documentation. The size of this lesion (cm^2) will be calculated, and the TLSS will be evaluated from this lesion.

To calculate the area of the Target Lesion the Investigator should measure once across its widest point and again at a point midway and perpendicular to the widest point. This should be done using the cm ruler provided. Measurements should be done to the nearest mm and reported in units of cm (i.e., reported as cm out to the first decimal place, not reported nor calculated in mm). These two values should be multiplied to give the total area of the Target Lesion (cm^2).

The Target Lesion should be used for all future evaluations and severity for individual signs and symptoms (scaling, erythema and plaque elevation).

To be eligible for inclusion at Visit 1, the patient must have all of the following:

- An affected BSA of 5 - 10% (Appendix A)
- A IGA score of 2 (mild) or 3 (moderate) (Appendix C)
- Target Lesion area of at least 5 cm^2
- Plaque Elevation Score  $\geq 2$  for the Target Lesion (based on TLSS score, Appendix B)

## **CONFIDENTIAL PROTOCOL**

A Randomized, Double-Blind, Placebo-Controlled, Parallel-Design, Multiple-Site Clinical Study to Evaluate the Efficacy and Safety of Desoximetasone Topical Spray, 0.15% (Taro Pharmaceuticals, U.S.A., Inc.) in Patients with Mild to Moderate Plaque Psoriasis

---

### **9.6.13 Health Status/Adverse Events**

At Visits 2, 3 and 4 patients will be questioned regarding any changes in their medical status since their previous visit. Any significant changes observed after randomization will be reported as adverse events.

## **9.7 Adverse Events**

The patients will be monitored throughout the study for any Adverse Events. AEs will be collected through both solicited and unsolicited means and subsequently coded in tabular form using the MedDRA (Version 17 or higher) Adverse Event Dictionary. The patients will be encouraged to report signs, symptoms, and any changes in health to the clinic staff. Severity of each AE will be determined by the staff based on observation and questioning of the patients. The Investigator will judge the relationship of the event to the study treatments. Adverse events should be followed up until they have resolved or stabilized.

### **9.7.1 Adverse Event Definitions**

Adverse Event: Any untoward medical occurrence in a patient or clinical investigation patient administered a pharmaceutical product and which does not necessarily have a causal relationship with treatment. An AE can therefore be any unfavorable and unintended sign, symptom, or disease, temporally associated with the use of a medicinal (investigational) product, whether or not related to this product. This includes events not seen at baseline, or worsened even if present at baseline.

Unexpected Adverse Event: An adverse event where the nature or severity of is not consistent with the applicable product information (e.g., Investigator's Brochure for an unapproved investigational product or package insert/summary of product characteristics for an approved product).

Adverse Drug Reaction: All noxious and unintended responses to a medical product related to any dose should be considered adverse drug reactions. The response to a 'medical product' means that a causal relationship between a medicinal product and an adverse event is at least a reasonable possibility, i.e., the relationship cannot be ruled out.

### **9.7.2 Severity of Adverse Event**

The severity of the adverse event will be graded by the Investigator using the following criteria as guidelines:

- **MILD**: Awareness of symptom but does not interfere with routine activities.
- **MODERATE**: Discomfort sufficient to interfere with routine activities.
- **SEVERE**: Impossible to perform routine activities.

### **9.7.3 Relationship of Adverse Event**

#### Relationship to the Study Product

- **NOT RELATED**: Any AE that is clearly not related to use of the study drug.

## **CONFIDENTIAL PROTOCOL**

A Randomized, Double-Blind, Placebo-Controlled, Parallel-Design, Multiple-Site Clinical Study to Evaluate the Efficacy and Safety of Desoximetasone Topical Spray, 0.15% (Taro Pharmaceuticals, U.S.A., Inc.) in Patients with Mild to Moderate Plaque Psoriasis

---

- POSSIBLE: The association of the AE with the study drug is unknown; however, a relationship between the drug and event cannot be ruled out.
- PROBABLE: There is reasonable temporal relationship between the use of the study drug and the AE. Based upon the Investigator's clinical experience, the association of the event with the study drug seems likely.
- DEFINITE: The AE occurs following the application of the study drug and it cannot be reasonably explained by any other known characteristics of the patient's clinical state, environmental or toxic factors, or other modes of treatment administered to the patient. It disappears or decreases upon discontinuation of the study medication and reappears on a re-challenge of the study drug.

